7.2. Interim Analyses and Summaries

At each analysis time point, the critical boundaries for the group sequential test will be derived from the predefined spending function(s) as described in Section 5.1. The calculations of boundaries will be performed using EAST.

7.2.1. Interim analysis for OS and PFS

Let $u_{OS}(t_1)$ and $u_{OS}(t_F)$ denote the upper critical boundaries based on the test statistics Z_{1_OS} and Z_{F_OS} for efficacy at the interim and the final analysis of OS, respectively, and let $l_{OS}(t_1)$ and $l_{OS}(t_F)$ denote the lower critical boundary for futility at the interim and final analysis of OS, respectively. For the final analysis of OS, $l_{OS}(t_F)=u_{OS}(t_F)$.

Let $u_{PFS}(t_1)$ and $u_{PFS}(t_F)$ denote the upper critical boundaries based on the test statistics Z_{1_PFS} and Z_{F_PFS} for efficacy at the interim and the final analysis of PFS, respectively, and let $l_{PFS}(t_1)$ and $l_{PFS}(t_F)$ denote the lower critical boundary for futility at the interim and final analysis of PFS, respectively. For the final analysis of PFS, $l_{PFS}(t_F)=u_{PFS}(t_F)$.

The critical values $u_{OS}(t_1)$ and $l_{OS}(t_1)$ for the interim analysis of OS are determined such as

$$P_0(Z_{1_OS} \geq u_{OS}(t_1)) = \alpha(t_1^{OS}) \quad \text{and} \quad P_a(Z_{1_OS} \leq l_{OS}(t_1)) = \beta(t_1^{OS}),$$

and critical values $u_{PFS}(t_1)$ and $l_{PFS}(t_1)$ for the interim analysis of PFS are determined such as

$$P_0(Z_{1_PFS} \geq u_{PFS}(t_1)) = \alpha(t_1^{PFS}) \quad \text{and} \quad P_a(Z_{1_PFS} \leq l_{PFS}(t_1)) = \beta(t_1^{PFS}),$$

where P_0 and P_a denote the probabilities under the null hypothesis and the alternative hypothesis, respectively, and $\alpha(t_1^{OS})$, $\beta(t_1^{OS})$ and $\alpha(t_1^{PFS})$, $\beta(t_1^{PFS})$ denote the α and β spent for interim analysis of OS and PFS, respectively, based on the predefined spending functions at information fraction t_1^{OS} and t_1^{PFS} , respectively. (t_1^{OS} is calculated as the ratio of the number of OS events observed at the time of the cut-off for the interim analysis and the total number of OS events targeted for the final analysis; t_1^{PFS} is calculated as the ratio of the number of PFS events observed at the time of the cut-off for the interim analysis and the total number of PFS events targeted for the final analysis).

The boundary for the final efficacy analysis of OS will be calculated such that

$$\alpha(t_1^{OS}) + P_0(Z_{1_OS} < u_{OS}(t_1), Z_{F_OS} \geq u_{OS}(t_F)) = 0.0115$$

The boundary for the final efficacy analysis of PFS will be calculated such that

$$\alpha(t_1^{PFS}) + P_0(Z_{1_PFS} < u_{PFS}(t_1), Z_{F_PFS} \geq u_{PFS}(t_F)) = 0.001$$

As described in Section 5.1.2, if the number of OS or PFS events in the final analysis deviates from the target number of OS or PFS events, the final analysis criteria will be determined as above taking into account the actual alpha spent at the interim analysis, the actual correlation between the two test statistics for OS, Z_{1_OS} and Z_{F_OS} and the actual correlation between the two test statistics for PFS, Z_{1_PFS} and Z_{F_PFS} , so that the overall 1-sided significance level across all analyses and comparisons is preserved at 0.025.

9. APPENDICES

Appendix 1. Immune-Related Adverse Events

The MedDRA PTs and clusters for irAEs are defined in the Safety Review Plan (SRP) for avelumab.

Immune-related AEs (irAEs) will be programmatically identified as outlined in Table 16. This case definition is hierarchical, ie, each step is only checked for patients and events that have already met the prior step.

Table 16. Case Definition for irAEs

Step	Selection Criteria	Additional Notes
1	Event selected based on a list of pre-specified MedDRA PTs within clusters. These are included in the SRP as Tier1 events (Immune-mediated xxxx). If AE matches the list then it is in for the next step	
2	AE onset during 1 st study drug administration or anytime thereafter through 90 days after last dose of study treatment.	This is regardless of start of new anti-cancer drug therapy and regardless of TEAE classifications
3	Answer in the AE eCRF page to ‘Was another treatment given because of the occurrence of the event’ is ‘YES’	
4	AE treated with corticosteroids or other immunosuppressant therapy. For endocrinopathies only: AE required hormone replacement	Look in the conmed pages for AE identifiers that match the AEs from Step 3. For each of such AEs if A) OR B) below are met then the AE is in for the next step A) conmed ATC code is in (H02A, H02B, H02C, D07, A01AC, S01BA, S01BB, L04AA, L04AB, L04AC, L04AD, L04AX) and AE PT is in any of the irAE clusters. B) conmed ATC code is in (H03A, H03B) and AE PT is in one of the irAE clusters associated with “Immune-mediated endocrinopathies”


5
	
A) No clear etiology (other than immune mediated etiology)
 
B) Histopathology / biopsy consistent with immune-mediated event
 
Event is in if [Answer to 5B1 and 5B2 is YES (regardless of answer to 5A)] OR [Answer to 5B1 is YES AND answer to 5B2 is NO AND answer to 5A is NO] OR [Answer to 5B1 is NO AND answer to 5A is NO]
	
A) From the AE eCRF page Is the AE clearly related to an etiology other than immune-mediated etiology? Yes / No If answer is Yes, check all that apply:
 
 • Underlying malignancy / progressive disease. • Other medical conditions. • Prior or concomitant medications / procedures. • Other. Specify. 
B) From the AE eCRF page B1) Was there a pathology /histology evaluation performed to investigate the AE? Y/N B2) If answer to the above is Yes, does the pathology/histology evaluation confirms an immune mediated mechanism for the AE? Y/N B3) If pathology / histology evaluation performed to investigate the AE, provide summary of relevant findings of the pathology /histology report. (Free Text)

----------	---	--

The data set associated with irAEs may be refined based on medical review. The final data set including any changes based on medical review (eg, addition of cases that are not selected by the programmatic algorithm) will be the basis of the irAE analyses.

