1.2.2.4. Efficacy and Safety in Patients with Ovarian Cancer

Single-agent avelumab activity at 10 mg/kg Q2W was evaluated in heavily pretreated epithelial ovarian cancer (EOC) patients in an ovarian-specific expansion cohort in Study EMR100070-001. Patients with ovarian cancer whose disease progressed on standard therapy were eligible. 75 patients were enrolled from Nov 2013 to Nov 2014. Median age was 62 years (range 38-84 years); ECOG performance status was 0 (41%) or 1 (59%); median number of prior therapies for locally advanced or metastatic disease (excluding adjuvant treatment) was 4 (range, 0-10). At the data cutoff of February 13, 2015, median duration of treatment with avelumab was 12 weeks (range 2-54 weeks), and 8 patients remained on treatment. Eight patients (10.7%, 95% CI, 4.7%, 19.9%) achieved an unconfirmed best objective response (BOR) of partial response (PR). Five out of 8 responses were ongoing at the time of data cutoff. Thirty-three (44%) patients had stable disease. Two additional patients had partial response by immune-related response criteria. Median progression-free survival was 11.4 weeks.

Avelumab was well-tolerated in the ovarian cancer expansion cohort (n=75). Table 3 demonstrates treatment-related adverse events observed in $\geq 5\%$ of patients. The following Grade 3 avelumab-related adverse events were observed in a total of 6 patients (8.0%): one event each of peripheral edema, localized edema, increased lipase, increased blood creatine phosphokinase, arthritis, myositis, hyperglycemia, anemia, tumor pain. There were no Grade 4 or 5 AEs related to avelumab reported in this cohort. Related serious TEAEs were observed in 3 patients (4.0%): Dyspnea (1), pyrexia (1), non-cardiac chest pain (1), flushing (1), localized edema (1), and peripheral edema (1). Immune-related TEAEs were seen in 8 patients (10.7%) and included hypothyroidism (5; 6.7%), arthritis (2; 2.7%), and myositis (1; 1.3%). No drug-related intestinal obstruction or perforations occurred. Discontinuation related to treatment with avelumab was reported in 9 patients (12.0%) [Pfizer/Merck KGaA data on file, cutoff 13 February 2015].⁴⁵

Table 3. Avelumab Treatment Related Adverse Events (Incidence $\geq 5\%$) in the Ovarian Cancer Cohort

Events (n=75)	Treatment-Related AEs, all grades*, n (%)
Any event	52 (69.3)
Fatigue	12 (16.0)
Chills	9 (12.0)
Nausea	8 (10.7)
Diarrhea	8 (10.7)
Infusion-related reaction	6 (8.0)
Rash	6 (8.0)
Vomiting	4 (5.3)

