8. Ongoing cardiac dysrhythmias of NCI CTCAE Grade ≥ 3 , atrial fibrillation of any grade, or QTcF interval >470 msec at screening (average of triplicate ECG).
9. Left ventricular ejection fraction (LVEF) <50% by MUGA or echocardiography.
10. Prior anthracycline-related cardiotoxicity or prior anthracycline exposure approaching the lifetime limit.
11. Prior organ transplantation including allogeneic stem-cell transplantation.
12. Known history of a positive test for human immunodeficiency virus (HIV) or acquired immunodeficiency syndrome (AIDS) related illness.

13. Active infection requiring systemic therapy.
14. Hepatitis B virus (HBV) or hepatitis C virus (HCV) infection at screening (positive HBV surface antigen or HCV RNA if anti-HCV antibody screening test positive).
15. Administration of a live vaccine within 30 days prior to study entry.
16. Current or prior use of immunosuppressive medication within 7 days prior to randomization. The following are exceptions to this exclusion criterion:
 - a. Intranasal, inhaled, topical steroids, or local steroid injections (eg, intra-articular injection);
 - b. Systemic corticosteroids at physiologic doses not to exceed 10 mg/day of prednisone or equivalent;
 - c. Steroids as premedication for hypersensitivity reactions (eg, CT scan premedication).
17. Active autoimmune disease that might deteriorate when receiving an immunostimulatory agents. Patients with diabetes type I, vitiligo, psoriasis, hypo- or hyperthyroid disease not requiring immunosuppressive treatment are eligible.
18. Known severe hypersensitivity reactions to monoclonal antibodies or liposomal preparations. Known hypersensitivity to any component of the Investigational Products.
19. Persisting Grade ≥ 2 toxicity related to prior therapy; however, Grade 2 sensory neuropathy or alopecia is acceptable.
20. Severe gastrointestinal conditions such as clinical or radiological evidence of bowel obstruction within 4 weeks prior to study entry, uncontrolled diarrhea in the last 4 weeks prior to enrollment, or history of inflammatory bowel disease.

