New onset of cardiac signs or symptoms and/or new laboratory cardiac biomarker elevations (eg, troponin, CK-MB, BNP) or cardiac imaging abnormalities suggestive of myocarditis	Withhold avelumab therapy Hospitalize In the presence of life threatening cardiac decompensation, consider transfer to a facility experienced in advanced heart failure and arrhythmia management Cardiology consult to establish etiology and rule-out immune-mediated myocarditis Guideline based supportive treatment as per cardiology consult* Consider myocardial biopsy if	If symptoms improve and immune-mediated etiology is ruled out, re-start avelumab therapy If symptoms do not improve/worsen, viral myocarditis is excluded, and immune-mediated etiology is suspected or confirmed following cardiology consult, manage as immune-mediated myocarditis

	recommended per cardiology consult.	
Immune-mediated myocarditis	
Permanently discontinue avelumab
 
Guideline based supportive treatment as appropriate as per cardiology consult*
 
1.0 to 2.0 mg/kg/day prednisone or equivalent
 
Add prophylactic antibiotics for opportunistic infections
	
Once improving, taper steroids over at least 1 month
 
If no improvement or worsening, consider additional immunosuppressants (eg, azathioprine, cyclosporine A)

*Local guidelines, or eg, ESC or AHA guidelines
 
ESC guidelines website: https://www.escardio.org/Guidelines/Clinical-Practice-Guidelines
 
AHA guidelines website: http://professional.heart.org/professional/GuidelinesStatements/searchresults.jsp?q=&y=&t=1001
		
Endocrine irAEs		
Endocrine Disorder	Initial Management	Follow-up Management
Grade 1 or Grade 2 endocrinopathies (hypothyroidism, hyperthyroidism, adrenal insufficiency, type I diabetes mellitus)	
Continue avelumab therapy
 
Endocrinology consult if needed
 
Start thyroid hormone replacement therapy (for hypothyroidism), anti-thyroid treatment (for hyperthyroidism), corticosteroids (for adrenal insufficiency) or insulin (for Type I diabetes mellitus) as appropriate
 
Rule-out secondary endocrinopathies (ie, hypopituitarism/hypophysitis)
	
Continue hormone replacement/suppression and monitoring of endocrine function as appropriate

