- The p-values and CIs reported are not adjusted for multiplicity and should be used for screening purposes only. The 95% CIs are provided to help gauge the precision of the estimates for the risk difference and should be used for estimation purposes only.

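### The irAE algorithm has no insulin code at Step 4, so immune-mediated type 1 diabetes treated with insulin alone is left to discretionary medical review

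*SAP*

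**What the plan says.** SAP 6.6.1 says irAEs are identified by the Appendix 1 method, using a preferred-term list fixed before database lock. On where that list is held, Appendix 1 states: "The MedDRA PTs and clusters for irAEs are defined in the Safety Review Plan (SRP) for avelumab". The Safety Review Plan was not supplied.

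Table 16 in Appendix 1 has five steps, and an event that fails one is not tested at the next. Step 4 concerns treatment. It admits events treated with corticosteroids or other immunosuppressants and adds a second limb: "For endocrinopathies only: AE required hormone replacement". Two code lists put this into effect:

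- **Item A**, for any irAE cluster: H02A, H02B, H02C, D07, A01AC, S01BA, S01BB, L04AA, L04AB, L04AC, L04AD, L04AX.
- **Item B**, for endocrine events: "conmed ATC code is in (H03A, H03B) and AE PT is in one of the irAE clusters associated with" immune-mediated endocrinopathies.

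After Step 5 the appendix allows the data set to be refined by medical review. It continues, "The final data set including any changes based on medical review (eg, addition of cases that are not selected by the programmatic algorithm", and makes that final set the basis of the irAE analyses.

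Protocol Appendix 9 includes type 1 diabetes among the endocrine irAEs in both its Grade 1 or 2 row and its Grade 3 or 4 row. The lower-grade row reads: "Start thyroid hormone replacement therapy (for hypothyroidism), anti-thyroid treatment (for hyperthyroidism), corticosteroids (for adrenal insufficiency) or insulin (for Type I diabetes mellitus) as appropriate".

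**The concern.** Step 4's code lists are narrower than its own criterion. Insulin given for new type 1 diabetes replaces a hormone, so the wording admits the event and the codes reject it. Because the steps are hierarchical, the event never reaches Step 5, where immune etiology is assessed.

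The irAE data set supplies the counts by cluster (overall, Grade 3 or higher, serious, leading to discontinuation or death) and the risk differences, confidence intervals and p-values against PLD in SAP 6.6.4. For this one event type, entry into those outputs rests on a review with no stated criterion, in an open-label trial.

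The other safety tables are only a partial backstop. Step 2 accepts onset up to 90 days after the last dose. The on-treatment period in SAP 5.2.7, which governs the TEAE and treatment-emergent SAE tables, ends at 30 days after the last dose or the day before new anti-cancer drug therapy, whichever is earlier. An insulin-treated case with onset on days 31 to 90 could therefore appear only in flagged listings.

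**Working it through.** The SAP gives no figure to reproduce. The check is a trace through Table 16, followed by a sizing.

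**Trace of type 1 diabetes with insulin as the only linked medication**

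1. Step 1 (term list): passes only if the Safety Review Plan includes the term. This cannot be verified.
2. Step 2 (onset window): passes if onset falls between first dose and 90 days after last dose.
3. Step 3 (other treatment given for the event): passes.
4. Step 4A: fails. Item A implements the corticosteroid and immunosuppressant limb, and no code in it is for insulin.
5. Step 4B: fails. Only H03A and H03B count.
6. Step 5: not reached.

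The code count is 12 in A plus 2 in B, 14 in all, with none beginning A10. Reading the codes assumes the standard ATC dictionary, in which insulins are A10A. The SAP prints no definitions, although SAP 6.5.4 uses ATC classes for concomitant medication.

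If the term is missing at Step 1, the event is still not selected. If a listed steroid or immunosuppressant is linked to the same event, item A is met and the event goes on to Step 5. The gap is therefore confined to insulin without such a drug.

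**Appendix 9 treatments set against the Step 4 codes**

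| Endocrine irAE | Treatment named in Protocol Appendix 9 | Code in Step 4 |
|---|---|---|
| Hypothyroidism | Thyroid hormone | H03A |
| Hyperthyroidism | Anti-thyroid drug | H03B |
| Adrenal insufficiency | Corticosteroid | H02 group |
| Type 1 diabetes | Insulin | none |

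Anti-thyroid drugs are not hormone replacement, so item B already reaches beyond the literal criterion. That makes the absence of insulin look like an oversight.

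**Size**

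- Arm size: 550 / 3 = 183.3. Two avelumab arms: 366.7, about 367.
- One case: 1 / 183.3 = 0.55 percentage points of one arm; 1 / 366.7 = 0.27 points of both.
- Protocol 1.2.2.4 reports 8 irAE patients among 75 in the ovarian avelumab cohort (5 hypothyroidism, 2 arthritis, 1 myositis) and no diabetes. Zero of 75 gives a one-sided 95% upper bound of 1 − 0.05^(1/75) = 3.9%. This is a bound, not an estimate.

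The documents give no rate, so the following rates are assumptions:

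| Assumed rate | Expected cases per arm (rate × 183.3) | Chance of none in 367, (1 − rate)^367 |
|---|---|---|
| 0.1% | 0.18 | 0.69 |
| 0.2% | 0.37 | 0.48 |
| 1% | 1.83 | 0.025 |

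**The case against.** The strongest reply is that the appendix already provides for this. Medical review may add cases the program missed, and the reviewed set is the one analysed, so the algorithm can be seen as a first screen. Nor is the algorithm free of judgement, since Step 5 uses the investigator's view of etiology in the same open-label trial. This softens the consequence but does not remove the fault. The review is permissive, the SAP gives no trigger for it, and it leaves the coded rule returning the wrong result. A rule might exist in the Safety Review Plan, which cannot be checked.

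Second, if the Safety Review Plan has no diabetes terms, the failure is at Step 1 and a new Step 4 code alone would do nothing. That is correct, and the fix has to cover it.

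Third, Appendix 9 lists insulin separately from thyroid hormone replacement, so hormone replacement might be read as excluding insulin. Appendix 9 also arrived with Amendment 2, after the final analysis, and the endocrine rows of the table it replaced name neither diabetes nor insulin. The protocol comparison is therefore supporting evidence. The main inconsistency is between Step 4's wording and its codes, and it rests on the ordinary reading of insulin as a hormone.

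Fourth, there may be no cases, and the outputs are exploratory. SAP 6.6.4 says: "The p-values and CIs reported are not adjusted for multiplicity and should be used for screening purposes only". Both points stand and limit the severity.

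**Conclusion.** The concern holds. As coded, Table 16 cannot select type 1 diabetes treated with insulin and no listed steroid or immunosuppressant; such a case enters the irAE data set only if medical review adds it. This conclusion rests on the standard meaning of the ATC codes. It does not depend on the Safety Review Plan's contents, which decide only whether the event is lost at Step 1 or Step 4.

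The effect is small and possibly nil: 0.55 percentage points of one arm per case, with the number of cases unknown. It is confined to the irAE summaries and their screening comparisons with PLD. The event still appears in the AE listings, and in the TEAE and SAE tables where it meets those definitions. OS and PFS are untouched. The gap should be corrected because it affects a pre-specified safety definition and is cheap to close, but it does not threaten the trial's main conclusions.

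**What to change.** Add an item C to Step 4: the concomitant-medication ATC code is in A10A, the medication is matched to the event by its AE identifier, and the preferred term is a type 1 diabetes term within the immune-mediated endocrinopathy clusters. Confirm that those terms are in the Safety Review Plan list used at Step 1, because item C has no effect without them.

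The identifier match, already used in Step 4, matters because exclusion criterion 17 in Protocol 4.2 states: "Patients with diabetes type I, vitiligo, psoriasis, hypo- or hyperthyroid disease not requiring immunosuppressive treatment are eligible". It keeps baseline insulin from counting. A worsening of pre-existing diabetes reported as an AE with linked insulin would still pass item C and would depend on the Step 5 etiology question.

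Keep medical review as a check, and list each case it adds or removes by arm, with the reason. As the final analysis has been completed, re-run Steps 4 and 5 and report the number of added cases by arm, including zero, noting any that review had already included.

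The cost is one line in Table 16 and its program, one check of the term list, and one re-run of the irAE derivation.

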Appendix 2. Infusion Related Reactions

For defining an AE as IRR the onset of the event in relation to the infusion of study drug and time to resolution of the event will be considered.

- All AEs identified by the MedDRA PT query describing signs and symptoms will be considered potential IRRs when onset is on the day of study drug infusion (during or after infusion) and the event resolved with end date within 2 days after onset.
- All AEs identified by the MedDRA PTs of Infusion related reaction, Drug hypersensitivity, Anaphylactic reaction, Hypersensitivity, Type 1 hypersensitivity, will be considered potential IRRs when onset is on the day of study drug infusion (during or after the infusion) or the day after the study drug infusion (irrespective of resolution date).

The list of MedDRA PTs for ‘IRRs SIGNS and SYMPTOMS’ and PTs ‘IRRs CORE’ are defined in the SRP for avelumab.

Infusion-related reactions (IRRs) will be programmatically identified as outlined in Table 17 or Table 18 (identified for IV drugs only).

Table 17. Case Definition for IRRs – IV study drugs Administered Alone

Condition	Selection criterion
If AE meets [1 AND 2] OR [3 AND (4A OR 4B)] then AE is classified as an IRR	
1	PT is included in the ‘IRRs SIGNS and SYMPTOMS’ list
2	
 • AE onset date = date of infusion of study drug AND • AE timing related to study drug (‘DURING’, ‘AFTER’) AND • AE outcome in (‘RECOVERED/RESOLVED’, ‘RECOVERED/RESOLVED WITH SEQUELAE’, ‘RECOVERING/RESOLVING’) AND • AE end date – AE onset date <=2
3	PT is included in the ‘IRRs CORE’ list
4A	
 • AE onset date = date of infusion of study drug AND • AE timing related to study drug in (‘DURING’, ‘AFTER’)
4B	AE onset on the day after infusion

Table 18. Case Definition for IRRs – IV Study Drugs Administered in Combination (eg, Doublets or Triplets)

Condition	Selection criterion
	
IRR can be associated with the first IV drug and/or subsequent IV drugs that are administered in combination. Without loss of generality assume triplet IV with D₁ administered first then D₂ then D₃. The IV study drug or drugs associated with the IRR need to be identified in the analysis data set to enable subsequent analysis.
 
The following are not sequential and an AE can be classified as an IRR associated with multiple D_j from one or more of I, II, III, IV, V below:
 
I - If the AE meets [1 AND 2A1] for a D_j then the AE is classified as an IRR associated with the D_j that meets the 2A1 criterion
 
II - If the AE meets [1 AND 2A2] for a D_j then the AE is classified as an IRR associated with the D_j and associated with D_{j+1} that meets the 2A2 criterion
 
III - If the AE meets [3 AND 4B] for any D_j then the AE is classified as an IRR associated with all D_j that meet the 4B criterion.
 
IV- If the AE meets [3 AND 4A1] for a D_j then the AE is classified as an IRR associated with the D_j that meets the 4A1 criterion
 
V- If the AE meets [3 AND 4A2] for a D_j then the AE is classified as an IRR associated with the D_j and associated with D_{j+1} that meets the 4A2 criterion

1	PT is included in the 'IRRs SIGNS and SYMPTOMS' list
2A1	
 • AE onset date = date of infusion of study drug D_j AND • AE timing related to study drug D_j ('DURING', 'AFTER') AND • [AE timing related to study drug D_{j+1} ('BEFORE') OR AE onset date < date of infusion of study drug D_{j+1}] AND • AE outcome in ('RECOVERED/RESOLVED', 'RECOVERED/RESOLVED WITH SEQUELAE', 'RECOVERING/RESOLVING') AND • AE end date – AE onset date <=2
2A2	
 • AE onset date = date of infusion of study drug D_j AND • AE timing related to study drug D_j ('DURING', 'AFTER') AND • AE timing related to study drug D_{j+1} ('DURING', 'AFTER') AND • AE outcome in ('RECOVERED/RESOLVED', 'RECOVERED/RESOLVED WITH SEQUELAE', 'RECOVERING/RESOLVING') AND • AE end date – AE onset date <=2
3	PT is included in the 'IRRs CORE' list
4A1	
 • AE onset date = date of infusion of study drug D_j AND • AE timing related to study drug D_j ('DURING', 'AFTER') AND • [AE timing related to study drug D_{j+1} ('BEFORE') OR AE onset date < date of infusion of study drug D_{j+1}]

090177e19142bcd4\Approved\Approved On: 09-Jul-2019 05:44 (GMT)

4A2	
• AE onset date = date of infusion of study drug D_J AND• AE timing related to study drug D_J ('DURING', 'AFTER') AND• AE timing related to study drug D_{J+1} ('DURING', 'AFTER')
4B	AE onset on the day after infusion of study drug D _J
